⁵The DTH skin test at prestudy will test the subjects' immunocompetency. Control antigens, Trichophyton Antigen and Candida antigen, will be administered id and the resulting induration will be ready at 48 - 72 hours post injection.

⁶ The DTH skin tests on weeks 5, 9 and 21 will test the DTH response to Mimotope P10s-PADRE. Trichophyton Antigen and Candida antigen will be administered id alongside Mimotope P10s-PADRE as control antigens to assess immunocompetency. DTH skin test indurations will be read at 48 – 72 hours post injection.

⁷ Visits must occur at set time points mentioned in the study calendar (+/- 3 days) with the exception of reading the skin test which must occur 48-72 hours post administration.

⁸ Concomitant medications will be collected from registration to end of treatment.

⁹ Post vaccine administration, the following vital signs will be monitored every 15 minutes (+/- 5 minutes) for one hour: blood pressure, temperature, and pulse.

¹⁰ Follow up visits shall begin with the next scheduled standard of care appointment and then shall occur every six months for five years and then yearly until death.

11. Criteria for Evaluation

Primary Objective – Safety:

- **Determination of DLT:** See Section 8, “Risks and Toxicities to be Monitored”. Any event that meets the dose limiting criteria will be determined a dose limiting toxicity.

Secondary Objectives – Immune Response:

- **Immunological Evaluation:** Serum will be collected at the Study Lab time points indicated in the study calendar in Section 10. Samples will be collected and stored by the UAMS Cancer Institute Tissue Bank following established Tissue Bank SOPs. IgM and IgG titers to TACAs will be evaluated by ELISA on TACA adhered to plates and FACS analysis of TACA adhered to liposomes. A positive TACA-directed immune response will be defined as an anti-TACA serum antibody titer of 1:40 for a baseline pre-vaccination titer of 0 or a \geq 4-fold increase over baseline titer > 0 (1, 11). Subjects will be judged to have had an adequate immune response if they have a positive TACA-directed immune response at any one of the first five designated time points following vaccine administration (Weeks 2, 3, 4, 7 and 9). The value of a booster immunization will be determined by anti-TACA IgM and IgG titers obtained from study labs collected on week 21.

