FACS analysis. Titer will be defined as the highest serum dilution yielding an $OD_{405} \geq 0.15$, in accordance with previous studies (1) or an MFI two standard deviations higher than background. A positive TACA-directed immune response will be defined as an anti-TACA serum antibody titer of 1:40 post-vaccination when the baseline pre-vaccination titer was 0, or a ≥ 4 -fold increase in titer post-vaccination when the baseline titer was greater than 0. The number and proportion of positive TACA-directed immune responses at each time point will be reported, both overall and by dose cohort. The number and proportion of subjects with at least one positive TACA-directed immune response will also be reported, both overall and by dose cohort. Medians and quartiles of titer will also be reported at each time point for any dose cohort of size 6.

To meet the secondary objective of analyzing the DTH response, we will measure the induration in mm across two diameters at the injection sites of the mimotope and control antigens. This will be done for each study subject at all indicated time points on the study calendar. An induration of >5 mm across at least one diameter will be considered a positive DTH response to that antigen at that time point. The number of subjects who show at least one positive DTH response to mimotope during the study will be reported as the number and proportion in each dose cohort. The number of positive DTH responses to mimotope at each time point will be reported as the number and proportion in each dose cohort. Positive DTH responses to the control antigens will be summarized the same way. Additionally, the two induration measurements per injection site, as well as their product (in mm^2), will be graphed as subject profiles over time, and summarized by antigen, dose group, and time as means and standard deviations.

To meet the secondary objective of determining sustainability of the immune response, the subject's TACA-directed immune titer at Week 19 will be compared to her TACA-directed immune titer at Week 9. The number and percentage of subjects with a sustained immune response will be reported in the aggregate and by dose cohort if more than one dose cohort is enrolled. In addition, the ratio of week-19 and week-9 titers will be plotted as dot plots and summarized as the mean, median and range.

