To meet the secondary objective of determining the immune response to the week-19 booster immunization, the subject's TACA-directed immune titer at Week 21 will be expressed as a ratio relative to her TACA-directed immune titer at Week 19. This ratio will be summarized as the mean, median and range, and plotted as dot plots. Subjects in whom the week-21 titer is more than 2-fold higher than the week-19 titer will be considered as having shown a boosted response to the booster immunization. The number and percentage of subjects showing a boosted response will be reported in the aggregate and by dose cohort if more than one cohort is enrolled.

To meet the exploratory objective of determining the vaccine's effect on the presence of CTCs at datable levels, the subject will be classified as Yes versus No for CTCs Detected, both at baseline and at Week 21, based on the outcomes of the assay described in paragraph d. of Section 9 above. The number and proportion of subjects with CTCs detected at each time will be reported in the form of a 2x2 contingency table for paired data, in order to facilitate the visualization of how many subjects change from Yes to No after completing the vaccination schedule.

Any deviations from the above analysis plan will be reported to the U.S. Army Medical

Research and Material Command Human Subjects Research Review Board (HSRRB), the Food and Drug Administration (FDA), and the UAMS Institutional Review Board

c. **Missing, Unused and Spurious Data:** Missing data will be treated as missing, and will not be imputed. All data collected will necessarily be reported to the FDA. Spurious data will be corrected at the source document. Any data documented as spurious that is unable to be corrected at the source will be treated as missing.

13. Registration Guidelines

Screening logs will be maintained by the study nurses. Subject registration will occur after the IRB-approved consent is signed and eligibility has been confirmed. The subjects will be registered in the CCTO and assigned a study number by the CRA. The study number will be used for identification of the research subject during the study.

14. Data Submission Schedule

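### Section 12.b averages titre ratios on the raw scale and does not say how a titre of 0 enters them; use a geometric mean ratio with a stated zero rule.

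*Combined protocol and SAP*

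**What the plan says.** For the booster, Section 12.b forms a ratio for each subject: "TACA-directed immune titer at Week 21 will be expressed as a ratio relative to her TACA-directed immune titer at Week 19". Then: "This ratio will be summarized as the mean, median and range, and plotted as dot plots". The sustainability paragraph of 12.b treats Week 19/Week 9 in the same way: "the ratio of week-19 and week-9 titers will be plotted as dot plots and summarized as the mean, median and range". Neither paragraph mentions a log scale or a geometric mean.

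The titre scale is also defined in 12.b: "Titer will be defined as the highest serum dilution yielding an" optical density at or above the cut-off, or a fluorescence signal above background. Zero is an accepted value there, because the positive-response rule has a separate branch: "titer of 1:40 post-vaccination when the baseline pre-vaccination titer was 0". No such branch exists for a Week 9 or Week 19 titre used as a denominator. The boosted classification also has none; it applies to "Subjects in whom the week-21 titer is more than 2-fold higher than the week-19 titer".

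Section 12.c is the nearest rule on data handling: "Missing data will be treated as missing, and will not be imputed". Section 11 names the antibody classes: "The value of a booster immunization will be determined by anti-TACA IgM and IgG titers". Section 12.b refers only to a single titre per subject.

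**The concern.** A titre is a dilution, and the plan's own response rules are fold changes. On such a scale a doubling and a halving cancel, but their raw ratios, 2 and 0.5, average 1.25. The raw mean therefore tends to suggest a rise when there is none.

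The zero gap makes this worse. By the titre definition, a serum that reaches the cut-off at no dilution has no titre, and dividing by it gives no ratio. Section 12.c does not settle the matter, because a non-reactive serum is a measured result, neither missing nor spurious. If the undefined ratio were nevertheless treated as missing, the handling would be lopsided: a subject going from 0 to 160 leaves the summary, while one going from 160 to 0 stays in with ratio 0.

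At stake is the continuous summary for the late booster, a listed secondary objective (Sections 2 and 4.b), and its counterpart for sustainability. Without a rule, the convention would be chosen after the titres are known.

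**Working it through.** The documents give no expected ratio, assay SD, dilution grid or share of zeros, so there is no planned figure to reproduce. Cohort sizes (3 or 6; nine subjects in all if no DLTs occur) come from Sections 7 and 12.a. Everything else below is assumed and shown as a range.

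**1. Results that need no assay assumption.** If nothing has changed and one value replaces 0 at both visits, the two titres X and Y are exchangeable. Then E[log(Y/X)] = 0. Also E[Y/X] = ½·E[Y/X + X/Y] ≥ 1, since r + 1/r ≥ 2 for any positive r. The geometric mean ratio (GMR) is centred on 1 on the log scale; the raw mean is not.

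**2. Size without zeros.** Simulated pairs with no true change, normal error at each visit, rounded down to a two-fold grid. The unrounded check is exp[(ln 2)² × SD²].

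| SD (two-fold steps) | Unrounded check | Expected raw mean | Cohort of 6: raw mean above 1 / below 1 |
|---|---|---|---|
| 0.25 | 1.03 | 1.02–1.07 | 52% / 28% |
| 0.5 | 1.13 | 1.17 | 65% / 25% |
| 0.7 | 1.27 | 1.32 | 72% / 23% |
| 1.0 | 1.62 | 1.68 | 79% / 19% |

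The last column assumes true titres spread evenly within a dilution step. If they are centred in the step, SD 0.25 gives 23% / 19%, so almost no asymmetry; the other rows barely move. The GMR falls above and below 1 equally often. Its own expectation at n = 6 is 1.00 to 1.09, not exactly 1.

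**3. Chance that the gap is met.** With a share p of zeros at the denominator visit, P(at least one undefined ratio) = 1 − (1 − p)^n.

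- p = 10%: 27%, 47% and 61% for n = 3, 6 and 9.
- p = 20%: 49%, 74% and 87%.

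**4. Direction with zeros, no true change.** Across 32 scenarios (between-subject SD 1 or 2 steps, the four within-subject SDs above, 10 to 60% zeros):

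- Zero denominators dropped, zero numerators kept: raw mean 1.04–1.53 at 10% zeros, 1.01–1.43 at 20%, 0.94–1.26 at 40%, 0.78–1.09 at 60%. It is below 1 in 9 of 32. The median ratio is 1.0 in 31 of 32 and 0.5 in one.
- 0 set to half the lowest dilution: raw mean about 1.04–1.63. Set to a quarter: 1.08–1.96.
- GMR: 1.00 in all 32 under either value.

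One case in full: lowest dilution 32, median titre 40, between- and within-subject SDs 1 and 0.7, 39.6% zeros. The raw mean is 0.95 with zero denominators dropped, and 1.22 or 1.51 with 0 set to half or a quarter of the lowest dilution.

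**5. Dependence on the value given to 0 (invented cohorts of 6).**

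| Pattern | Value for 0 | Raw mean | GMR | Median |
|---|---|---|---|---|
| A: Week 19 = 0, 0, 0, 40, 80, 160; Week 21 = 0, 80, 160, 80, 80, 160 | 20 / 10 / 5 | 2.83 / 4.83 / 8.83 | 2.00 / 2.52 / 3.17 | 1.5 throughout |
| W: two subjects 160 to 0, four unchanged | 20 / 10 / 5 | 0.71 / 0.69 / 0.68 | 0.50 / 0.40 / 0.31 | 1.0 throughout |
| Z: three subjects 0 to 40, three 40 to 320 | 20 / 10 | 5.0 / 6.0 | 4.0 / 5.66 | 5.0 / 6.0 |

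For A at 20 the ratios are 1, 4, 8, 2, 1, 1: raw mean 17/6 = 2.83, GMR 2^(6/6) = 2.00. With the three zero-denominator subjects left out of A (n = 3), the raw mean is 1.33, the GMR 2^(1/3) = 1.26 and the median 1.0.

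**6. Boosted count.** Example C: Week 19 = 0, 40, 40, 80, 80, 160; Week 21 = 40, 80, 40, 80, 40, 160. On measured titres, Week 21 > 2 × Week 19 holds for 1 of 6. With 0 set to 20 the first ratio is exactly 2.0 and the count is 0 of 6; with 10 or 5 it returns to 1 of 6.

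**The case against.** The strongest reply is that the plan already holds a robust summary. The median is not biased upward, every ratio is to be plotted, and with cohorts of 3 or 6 a reader sees the individual subjects. Section 12.a calls the immunogenicity assessment qualitative. Tables 1 to 3 count DLTs only, and although Section 2 mentions immune response at Week 9, both ratios need a Week 19 sample and cannot feed that decision. All this stands and keeps the point small. It does not close the gap, because the median too is undefined until a zero rule exists: in A it is 1.0 or 1.5 depending on the convention.

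A second reply is that zeros at Weeks 9 and 19 are an inference, since four doses are scheduled by then. That is correct, and the share of zeros is unknown. But Section 3 itself describes limited anti-LeY responses to earlier conjugate vaccines, and the Week 19 serum is drawn before the booster, 12 weeks after the Week 7 dose.

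A third reply is that replacing 0 by a constant would harm the boosted count, which works on measured titres. Example C bears this out, so the constant should stay out of that rule.

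**Conclusion.** The point holds as a minor improvement to the analysis. The raw mean is off-centre for a multiplicative measure, and 12.b leaves a foreseeable value, 0, without a rule. The upward bias among positive titres and the centring of the log ratio follow from exchangeability alone. The sizes (1.02 to 1.68 without zeros, roughly 0.78 to 1.96 with them) rest on assumed SDs, dilution grids and zero shares. At the smallest SD, with centred alignment, the effect is negligible.

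A reader might go further and infer that the GMR is also less sensitive to the value chosen for 0. That is not supported. It is true in pattern A, where a few zero denominators have large rises. It reverses in W, which is a natural pattern for the Week 19/Week 9 ratio, and in Z. The documents give nothing that says which pattern to expect. Nor do they support reading 12.c as already excluding these subjects, or reading the plan as relying on the raw mean alone.

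**What to change.** Amend 12.b as follows.

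1. For Week 21/Week 19 and Week 19/Week 9, replace the raw mean ratio with the geometric mean ratio from log2 titres. Keep the median, range and dot plots.
2. For these ratio summaries only, give non-reactive sera one prespecified value at both visits, tied to the lowest dilution tested (for example half of it). State that this represents a measured result below range and is not imputation under 12.c. Include every subject with both samples.
3. Repeat the GMR with a second value (for example a quarter) and with subjects who have 0 at either visit left out, giving n each time, and list those subjects. Dropping on either visit is necessary because the log of a zero numerator is undefined.
4. Keep the boosted rule on measured titres: Week 21 > 2 × Week 19. State that 0 followed by any positive titre counts as boosted and that 0 followed by 0 does not. The substituted value plays no part.
5. Report IgM and IgG separately, in line with Sections 4.b and 11.

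The cost is a few lines of text and no new data. Two drawbacks remain. The GMR still moves with the chosen value, which item 3 puts on view. A subject can also be boosted while her displayed ratio is only 2.0 (example C with 0 set to 20), which the listing explains.
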